For the Usual Care clinics, all measurements will be obtained on a quarterly basis through the BP Track surveillance project (a companion study), with measurement periods set to end at the end of each calendar quarter (Mar 31, June 30, Sept 30, Dec 31). The primary outcome will compare the metrics obtained at baseline, defined as the measurement period ending June 30, 2019 for all Usual Care sites, and at 6 months, defined as the measurement period ending Dec 31, 2019, for all Usual Care sites. These fixed dates were set under the assumption that the BP MAP intervention clinics will all launch their interventions within the window of May 15, 2019-August 31, 2019, and that this is therefore the most appropriate single 6-month comparison period, acknowledging that it will not correspond precisely to the same calendar time period as all of the intervention clinics (which will launch at different times), and that the measurement periods will be offset by 6 months vs. 7 months for the intervention clinics due to practical constraints.

For added clarity, these measurement periods are illustrated in the Figure below, with an arrow indicating an example launch date of June 15, 2019 for an Intervention Clinic.

Below we list the outcome measures of interest. Additional technical details for how the queries were constructed for each measure are provided in the supplemental materials.

- 1) Change in % BP Control at 6 months (primary outcome). Our primary outcome will be clinic-level change in the proportion of patients with controlled BP from baseline to 6 months after the start of the intervention. We define BP control according to NQF 0018 as the percent of eligible patients (defined above) with SBP <140 mmHg and DBP < 90 mmHg, based on measurements obtained at the most recent ambulatory clinical encounter at baseline (using the lowest measures of SBP and DBP at that encounter) and similarly at the 6-month time point after initiation of the intervention.

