Secondary outcomes will include nine additional EHR-derived clinic-level metrics relevant to BP control. These metrics include alternate measures and BP control and improvement, as well as process and proxy measures aligned to the domains of the M.A.P. program including: indicators of BP measurement accuracy, medication intensification, average SBP reduction after medication intensification, and repeat visit within 4 weeks after a visit with uncontrolled HTN. Each metric below (and the primary outcome) will be measured as a change from baseline to 6 months (our primary time point), and change from baseline to 12 and 18 months. We will assess each metric overall (in all eligible patients) and within subgroups defined in Table 3.

- 2) BP Control to 2017 Guideline Goal, %. This alternative overall measure of BP control is identical to Metric 1, except that attainment of BP Control is defined by lower thresholds for blood pressure (SBP < 130 mmHg and DBP < 80 mmHg), as per the goal stated in the 2017 ACC/AHA Hypertension Guideline.
- 3) Improvement in blood Pressure, %. This overall measure of BP improvement defines BP improvement as either a reduction of 10 mmHg in SBP or achievement of SBP that is “adequately controlled” (SBP < 140 mmHg) over a period of 3 months, among hypertensive patients not previously controlled.
- 4) Confirmatory repeated blood pressure measurement, %. This process measure is designed to capture the practice of repeating a blood pressure measurement in the same visit when the first measurement done in clinic is high (SBP>140 mmHg or DBP>90 mmHg).
- 5) Medication intensification, %. This process measure captures the proportion of visits where BP is uncontrolled where a medication is ordered that is of a different class of medications than had previously been used. Note that this explicitly does not give credit for ordering a simple refill or medication dose increase, or use of a different medication in the same class.
- 6) Repeat visit in 4 weeks after uncontrolled HTN, %. This process measure captures the proportion of persons who had uncontrolled HTN who made a subsequent outpatient visit within the following 4 weeks.
- 7) Average SBP reduction after medication intensification, mmHg defined as the change in SBP observed between a visit with a medication intensification to the subsequent visit.

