### **Analysis Plan**

Overview: We will use an unadjusted difference-in-differences analytic approach to testing comparative effectiveness hypotheses, weighting for differences in cluster size. Despite expected between-clinic differences in baseline characteristics and BP control (especially in the non-randomized comparison with Usual Care control organizations), the difference-in-differences approach provides some protection against confounding because the outcome being compared is a within-clinic change score, as described below. We will first conduct 3 pairwise primary hypothesis tests (adjusting for multiple comparisons), as described below. We will then conduct a series of exploratory analyses of secondary outcomes, sensitivity analyses adjusting for baseline clinic-level characteristics, subgroup analyses to examine heterogeneity of effect, and exploratory mediation analyses to understand the mechanisms by which the full-support intervention might provide greater effectiveness.

Differences-in-differences analytic approach: We will calculate difference-in-differences through the following steps:

1. Use clinic-level metrics (e.g., % BP control) at baseline for each clinic before the intervention starts ( $t_0$ ) and then including the 6th full month of the intervention (" $t_6$ ", noting that the period will actually be 7 months offset for the Intervention Clinics and 6 months for the Usual Care Clinics; see Outcomes and Measurements, above)
2. Calculate the clinic-level pre-post difference in the metric ( $t_6 - t_0$ )
3. Calculate the mean pre-post difference in each treatment group, the between-group difference of differences, both with 95% confidence intervals, and compare the 20-28 pre-post differences by arm using weighted linear regression; observations will be weighted by the inverse of the site-specific variances of the change scores, which will be approximated using the site-specific sample size and level of the time-specific metrics, and the average correlation of the pre- and post-metrics across clinics. Weights will be normalized to sum to the total number of clinics in the Arm 1 vs. Arm 2 comparisons (and to the number of included clinics plus the number of participating PCORnet datamarts for the comparisons of each Arm with Usual Care).

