**Sensitivity analyses:** In a sensitivity analysis, we will perform multivariable linear regression analyses to compare clinic-level pre-post differences in our primary and secondary outcomes. The regression models will adjust for health system as well as for whether the clinic was engaged in BP HOME, a concurrently running individual-level randomized trial that will provide home blood pressure monitoring devices to participating patients with a high blood pressure reading in clinic. We will also consider linear mixed models (LMMs) for repeated changes in the summary outcome measures, adjusting for age, sex and race-ethnicity. In particular, for each clinic we will calculate monthly values of the metric  $(t_i - t_0)$ , for follow-up month  $i = 1, \dots, 6$ , within strata jointly defined by age, sex, and race-ethnicity, as well as corresponding within-stratum weights as described above, then estimate the effect of treatment adjusted for stratum, using an LMM that includes treatment assignment, month as categorical, the interaction of these two factors, and stratum. With a view towards model simplification, likelihood ratio testing will be used to determine whether age, sex, and race/ethnicity as additive factors adequately capture the stratification effects. We will: (1) present month-specific treatment effects with 95% confidence intervals (CIs); (2) test for heterogeneity in the monthly treatment effects across months; (3) summarize the treatment effect by the average of the month-specific effects also with a 95% CI, if the test for heterogeneity is not statistically significant ( $P>0.05$ ); and (4) otherwise, use orthogonal contrasts to check for linear and quadratic trends in the monthly effects.

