**Table 3. Subgroups for HTE analysis**

Age: 18-44 vs. 45-64 vs. 65+

Race/ethnicity: NH White vs. NH Black vs. NH Asian vs. Hispanic (any race) vs. Other
Sex: Male vs. Female
Enrolling CDRN
HTE – Heterogeneity of treatment effects
NH – Non-Hispanic

**Exploratory Mediation analysis:** As many of our secondary outcomes are presumably process measures in the causal pathway to achieving BP control, we will perform a mediation analysis to understand the degree to which the potential added benefit of the Full Support intervention on BP control is explained by changes in the process measures. We will perform a mediation analysis using nested linear regression models for the effect of randomization assignment (i.e. Full Support vs. Self-Guided) on clinic level pre-post differences in percent control, first omitting, then adding each of our proposed mediators to the base model. The hypothesized process mediators will include pre-post changes in BP measurement accuracy, medication intensification, and average SBP reduction after medication intensification, and repeat visit in 4 weeks after uncontrolled HTN. These analyses will be implemented using the Paramed module in Stata statistical software  to calculate natural direct effect (NDE) of full-support on BP control and the natural indirect effect (NIE) through each mediator. The total causal effect (TCE) is the sum of the NDE and NIE. Dividing each NIE by the TCE will calculate the proportion of the causal effect explained by each mediator.

**Additional exploratory analyses:** We will explore temporal patterns in the effect of randomization assignment using linear mixed models for repeated clinic-level changes since baseline in primary and secondary outcomes assessed at 6, 12, and 18 months. These models will include random effects for clinic, as well as fixed effects for treatment assignment (as a categorical variable), and their interaction. Heterogeneity of treatment effects across time will be tested using a 2 degree-of-freedom chi-square test; in addition, a chi-square test for linear trend will be obtained by comparing the fitted treatment assignment effects at 6 and 18 months.

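### Metric 7 averages SBP change only over intensification visits, without accounting for SBP at that visit, so it can fall with no change in drug effect; it is also a doubtful process mediator

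*Combined protocol and SAP*

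**What the plan says.** All references are to the combined protocol and SAP, section III, Methods.

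- **Metric 7** (Outcomes and measurements, item 7) is "defined as the change in SBP observed between a visit with a medication intensification to the subsequent visit". The text states no reference SBP, no interval to the second visit and no comparison group.
- **Metric 5** "captures the proportion of visits where BP is uncontrolled where a medication is ordered that is of a different class of medications" than before. **Metric 6** "captures the proportion of persons who had uncontrolled HTN who made a subsequent outpatient visit within the following 4 weeks". Both are outcomes that the programme hopes to move.
- **Main analysis** (Analysis Plan, Overview): "We will use an unadjusted difference-in-differences analytic approach to testing comparative effectiveness hypotheses".
- **Sensitivity analyses**: "The regression models will adjust for health system as well as for whether the clinic was engaged in BP HOME". The mixed model adds strata of age, sex and race-ethnicity. SBP at the intensification visit appears in neither.
- **Exploratory Mediation analysis**: "The hypothesized process mediators will include pre-post changes in BP measurement accuracy, medication intensification, and average SBP reduction after medication intensification", plus return within 4 weeks. Each indirect effect is divided by the total effect to give a proportion explained.
- **Primary outcome** (item 1): control is "based on measurements obtained at the most recent ambulatory clinical encounter at baseline", and in the same way at 6 months.

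**The concern.** Intensification happens after randomisation and is something the intervention tries to increase. The patients and visits that enter Metric 7 may therefore differ by arm for reasons other than drug response, and randomisation does not protect the comparison. Taking differences from baseline does not help, because the visit mix can shift between baseline and follow-up.

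The raw change is the drug effect plus regression to the mean, and the second part grows with the index SBP (the reading at the intensification visit). If clinicians begin to act on milder readings, mean index SBP drops and Metric 7 drops with it, although the drugs work as before and more patients are treated. A reader could take that for a weaker treatment response.

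The mediation use raises a separate issue. Metric 7 is a change in BP rather than an action by the clinic. When the visit after intensification is also the patient's most recent encounter, its second reading can be the one that decides the primary outcome.

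**Working it through.** The plan gives no figure for Metric 7. Its power figures concern the primary outcome and are not in question here. Every SBP input below is an assumption; only the launch example and window dates come from the documents.

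**1. Formula.** Let usual SBP have mean μ and between-patient SD σb, visit-to-visit SD σw, and a constant drug effect δ. With intensification depending only on the index reading x:

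Metric 7 = δ + [σw² / (σb² + σw²)] × (mean x at intensification − μ)

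**2. Two regimes**, δ = 8 mmHg. Probability of intensification at x of 140-149, 150-159 and 160 or more:
- A: 0.05 / 0.15 / 0.30
- B (milder elevations treated more): 0.30 / 0.35 / 0.40

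Example with μ = 142, σb = 12, σw = 11. The factor is 121 / (144 + 121) = 0.457. Simulated mean index SBP is 160.1 under A and 154.8 under B.
- A: 8 + 0.457 × 18.1 = 16.3
- B: 8 + 0.457 × 12.8 = 13.9
- Fall: about 2.4 mmHg, with the drug effect unchanged.

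**3. Dilution by the 12-month window.** For the plan's example launch of June 15, the 6-month window runs January 1 to December 31, so about 5.5 of its 12 months precede launch. Intensification rates among uncontrolled visits are 0.144 (A) and 0.341 (B). The visit weights are 5.5 × 0.144 = 0.792 and 6.5 × 0.341 = 2.217, so

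(0.792 × 16.27 + 2.217 × 13.86) / 3.009 = 14.49

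The fall is 16.27 − 14.49 = 1.78 mmHg.

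**4. Uniform rise of 5 points per band** (0.10 / 0.20 / 0.35). Mean index SBP is 158.5, so Metric 7 = 8 + 0.457 × 16.5 = 15.5, a fall of about 0.75 mmHg.

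**5. Proportional rise** (every probability doubled). Mean index SBP does not change, so the fall is 0.

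**6. All eight settings (mmHg):**

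| μ; σb/σw | A | B | Fall, pure regimes | Fall, 12-month window | Fall, uniform 5-point rise |
|---|---|---|---|---|---|
| 142; 12/11 | 16.26 | 13.85 | 2.41 | 1.78 | 0.75 |
| 142; 10/10 | 15.93 | 13.48 | 2.45 | 1.85 | 0.81 |
| 142; 14/9 | 13.41 | 11.85 | 1.56 | 1.14 | 0.48 |
| 142; 12/14 | 19.67 | 16.47 | 3.20 | 2.31 | 0.95 |
| 135; 12/11 | 18.23 | 15.87 | 2.36 | 1.80 | 0.81 |
| 135; 10/10 | 17.99 | 15.70 | 2.29 | 1.79 | 0.85 |
| 135; 14/9 | 14.64 | 13.12 | 1.52 | 1.15 | 0.51 |
| 135; 12/14 | 22.23 | 19.01 | 3.21 | 2.40 | 1.03 |

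Another simulation run put the top of the last column at about 1.1.

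**7. A second model** (mean 138, σb 14, drug effect 9 mmHg; intensification at 10% of readings of 140-154 and 30% at 155 or above, moving to 30% of both). Metric 7 goes from 11.7 to 11.1 at σw = 6, from 15.6 to 14.1 at σw = 10 and from 17.9 to 15.8 at σw = 12. BP control rises by about 1 to 2.5 points. With no visit-to-visit variation the fall is 0 (9.0 in both).

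**8. Standardisation.** Averaging band-specific changes with common weights gives 16.26 under both A and B in the example. In the second model at σw = 10 it gives 14.08 under both.

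**9. Shared readings.** For otherwise identical clinics of an assumed 1,000 patients, the correlation of Metric 7 with the control rate is 0.07-0.08 with no shared readings. It is 0.17-0.25 if every post-intensification visit is also the most recent one.

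**The case against.** A reader might infer that Metric 7 will make the better arm look worse. The documents do not support that. Nothing in them says Full Support will shift treatment towards milder readings, and a proportional rise moves Metric 7 by about nothing. A larger true drug effect can also offset the fall: 2 mmHg more in the better arm turns the falls of 1.5 to 3.2 mmHg into anything from a fall of 1.2 to a rise of 0.5. The largest figures rest on a strong scenario, a six-fold rise at 140-149 against 1.33-fold at 160 or more. These objections stand, and the claim is therefore conditional.

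A mean of 142 implies about 45% of patients below 140 mmHg, whereas the plan's pilot started at 65.6% control. This is a fair calibration point but not decisive, since the falls at a mean of 135 are similar.

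A reader might also infer that the mediation result is circular. That is too strong. The share of overlapping readings is unknown, the correlation stays modest even with complete overlap, and an SBP fall after intensification is plausibly on the causal path. Selection could push the indirect effect down and shared readings push it up; no net direction has been shown.

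The plan labels the secondary and mediation analyses exploratory, and Metrics 1, 3, 5 and 6 would be reported alongside. Query details sit in supplemental materials outside the reviewed text and might restrict index SBP or interval. These points limit the stakes. They do not remove the gap in the stated plan.

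**Conclusion.** The point holds in conditional form. As written, Metric 7 compares arms over a set of visits that the intervention may change, with no allowance for SBP at those visits. It can therefore fall without any change in drug effect if two conditions are met: the added intensification falls disproportionately on milder elevations, and there is visit-to-visit variation (or a response that depends on index SBP). The ranges in the working rest on assumed SBP distributions, assumed intensification probabilities and a constant drug effect. They also leave out visits uncontrolled on DBP alone, and assume that Metric 7 uses Metric 5's definition of intensification.

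Listing Metric 7 among process mediators is doubtful because of what it measures and the reading it can share with the outcome. The harm to the mediation result cannot be sized from the documents.

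The consequence is confined to exploratory results. The primary outcome, its tests and its power are untouched.

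**What to change.** 1. For Full Support versus Self-Guided, report Metric 7 standardised to a common index-SBP distribution beside the raw metric. Query the mean change and the count in bands of below 140 (visits qualifying on DBP alone), 140-149, 150-159 and 160 or more. Merge sparse bands, and weight by the distribution across all active clinics at baseline.
2. Report index SBP and the interval to the next visit by arm, since Metric 6 may change that interval and banding does not address it.
3. Remove Metric 7 from the mediator list, or label its indirect effect as descriptive and not causal. Keep the true process measures as mediators.
4. Extend the standardisation to Usual Care only if BP TRACK can supply the bands.

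The cost is an added banding and interval summary in the aggregate query and a short edit to the mediation text. The downsides are sparse bands in small clinics and one fewer exploratory mediator. Standardisation also has a limit: it will not fully remove a fall caused by less noisy BP measurement. In the second model, reducing visit SD from 12 to 10 mmHg with treatment rules unchanged lowers raw Metric 7 from about 17.8 to 15.6 mmHg. Even the standardised figure should therefore be read with care.

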### **Analysis Plan**

Overview: We will use an unadjusted difference-in-differences analytic approach to testing comparative effectiveness hypotheses, weighting for differences in cluster size. Despite expected between-clinic differences in baseline characteristics and BP control (especially in the non-randomized comparison with Usual Care control organizations), the difference-in-differences approach provides some protection against confounding because the outcome being compared is a within-clinic change score, as described below. We will first conduct 3 pairwise primary hypothesis tests (adjusting for multiple comparisons), as described below. We will then conduct a series of exploratory analyses of secondary outcomes, sensitivity analyses adjusting for baseline clinic-level characteristics, subgroup analyses to examine heterogeneity of effect, and exploratory mediation analyses to understand the mechanisms by which the full-support intervention might provide greater effectiveness.

Differences-in-differences analytic approach: We will calculate difference-in-differences through the following steps:

1. Use clinic-level metrics (e.g., % BP control) at baseline for each clinic before the intervention starts ( $t_0$ ) and then including the 6th full month of the intervention (" $t_6$ ", noting that the period will actually be 7 months offset for the Intervention Clinics and 6 months for the Usual Care Clinics; see Outcomes and Measurements, above)
2. Calculate the clinic-level pre-post difference in the metric ( $t_6 - t_0$ )
3. Calculate the mean pre-post difference in each treatment group, the between-group difference of differences, both with 95% confidence intervals, and compare the 20-28 pre-post differences by arm using weighted linear regression; observations will be weighted by the inverse of the site-specific variances of the change scores, which will be approximated using the site-specific sample size and level of the time-specific metrics, and the average correlation of the pre- and post-metrics across clinics. Weights will be normalized to sum to the total number of clinics in the Arm 1 vs. Arm 2 comparisons (and to the number of included clinics plus the number of participating PCORnet datamarts for the comparisons of each Arm with Usual Care).

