#### Study Population and Setting

We will recruit Active Clinics from REACHNet and ADVANCE, two of the 10 Clinical Data Research Networks (CDRNs) that comprise PCORnet. We chose these two CDRNs to focus clinic recruitment in safety net clinics and to boost numbers of underserved populations and enhance power to detect heterogeneity of treatment effects. We are targeting clinics that have varied racial/ethnic composition with substantial proportions of Hispanic and Black patients, and patients with lower socioeconomic status. Usual Care Clinics will come from other CDRNs within PCORnet.

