### **Randomization**

We will use a random number generator to randomize 10-14 Active Clinics to the Full Support Arm and 10-14 Active Clinics to the Self-Guided Arm. Randomization will be stratified (and balanced within strata) by CDRN and by participation (or not) in BP HOME, a concurrently running individual-level RCT that will provide home blood pressure monitoring devices to participating patients with a high blood pressure reading in clinic. As this is a real-world intervention that clinics will have to implement, they will not be blinded to the randomization.

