**Subgroup analysis to test for heterogeneity of treatment effects (HTE):** We will produce clinic-level subgroup-specific analyses limited to subgroups defined by the characteristics listed in Table 3 (with imputation as described above), and test for interactions by intervention group (as well as with Usual Care) and subgroup categories. We hypothesize that the BP Control effect from the Full-Support intervention relative to Self-Guided and Usual Care groups will be smaller in patients who are younger, male, and Black given published BP control difficulties in these patients. We will also specifically test for an interaction between treatment group and enrolling CDRN, given health IT infrastructures may differ by CDRN in ways that can interact with the effectiveness of the interventions. All subgroup analyses will be reported.

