**Data source, collection, management, and safety:** Consistent with principles of pragmatic clinical trials, we will use EHR data for patient identification and assessment of intervention implementation and outcomes. Both interventions (and usual care) are consistent with standard of care. Therefore, both the interventions and data collection in this study carry minimal risk to patients. We will leverage the data infrastructure and resources in the PCORnet Common Data Model to collect de-identified, clinic-level aggregate data needed for analysis. Additional details on the PCORnet Common Data Model procedures for data collection and linkage, and data management and safety are described elsewhere.

**Sample size and power:** Preliminary data from “Wave 2” implementation of the M.A.P. Program by AMA in 16 clinics shows average pre-post improvements (without a control group) in BP control of 6.8% (65.6%-->72.4% overall) +/- 4.4% (standard deviation of change in control rate). Assuming negligible change in the Self-Guided arm, standard sample size calculations show that we will have 83% power to detect a difference in differences of 6% in the BP control rate (or 92% power for 7% difference) between Self-Guided and Full-Support arms with 10 clinics randomized to each arm of the study; these results were confirmed using simulations. Power will be higher for comparisons of the Self-Guided and Full-Support groups with the large Usual Care comparison group in PCORnet under similar effect-size

assumptions. For the HTE analysis comparing the difference in differences between the 10 clinics in CDRN 1 (5:5 in each arm) and the 10 clinics in CDRN 2 (5:5 in each arm), we expect to have 80% power to detect an interaction effect (i.e., the difference in the difference in differences) of 12% in the BP control rate. Corresponding minimum detectable interaction effects would be 15%, 13%, and 12% for demographic subgroups comprising 20%, 30%, and 40% of the overall population.

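### Randomisation is stratified by CDRN and BP HOME, but the primary Full Support vs Self-Guided regression contains neither factor, so precision is lost if they predict change in control

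*Combined protocol and SAP*

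**What the plan says.** - **Randomization:** "Randomization will be stratified (and balanced within strata) by CDRN and by participation (or not) in BP HOME".
- **Analysis Plan, overview:** "We will use an unadjusted difference-in-differences analytic approach to testing comparative effectiveness hypotheses, weighting for differences in cluster size".
- **Analysis Plan, difference-in-differences step 3:** the plan will "compare the 20-28 pre-post differences by arm using weighted linear regression", with inverse-variance weights. No covariate is listed.
- **Sensitivity analyses:** "The regression models will adjust for health system as well as for whether the clinic was engaged in BP HOME". CDRN is not named here.
- **Subgroup analysis (HTE):** "We will also specifically test for an interaction between treatment group and enrolling CDRN", the reason being "given health IT infrastructures may differ by CDRN in ways that can interact with the effectiveness of the interventions".
- **Study Population and Setting:** "Usual Care Clinics will come from other CDRNs within PCORnet". This matters for which tests can be adjusted.

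The plan gives no reason for leaving the stratification factors out of Test 1, and does not say whether health systems are nested within CDRNs.

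**The concern.** Stratifying makes the arms comparable on CDRN and BP HOME. An analysis that ignores the strata does not take full credit for that. Between-stratum variation no longer contributes to the error of the balanced comparison, but the arm-only model still counts it as residual noise. The reported standard error is then too large, the interval too wide and the test conservative.

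A second effect comes from the weights. The design balances the number of clinics per arm within strata, not their inverse-variance weight. With unequal weights the unadjusted estimate can carry part of a stratum difference that stratification was meant to remove.

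Test 1 is the only randomised primary comparison. It rests on 20 to 28 clinics and has little power to spare at its planned threshold, so forgone precision matters here.

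**Working it through.** **Inputs from the documents.** SD of clinic change 4.4 points; effect 6 points (or 7); 10 clinics per arm (Sample size and power); threshold 0.04 for Test 1 (Primary hypothesis tests). Ten clinics and 5:5 arms per CDRN follow the power section: "the 10 clinics in CDRN 1 (5:5 in each arm").

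**Assumptions.** Two-sided testing. R², the share of the total variance 4.4² explained by additive CDRN and BP HOME effects, is not in the documents and is varied from 0 to 0.3. BP HOME participation is not given either; stratum cells of 6/4/6/4 (28 clinics: 8/6/8/6) are assumed.

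**1. The plan's own figure.** For a two-sample t-test with 18 df, the noncentrality is 6 / (4.4 × √(2/10)) = 6 / 1.968 = 3.05.
- At alpha 0.05, power is 82.2% for 6 points and 92.0% for 7. The stated 83% and 92% are reproduced within 2 points.
- At the planned 0.04 the t-based figures are 79.2% and 90.1%.

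**2. Why the unadjusted standard error is too large (equal weights, R² = 0.2).**
- Variance within strata: 0.8 × 4.4² = 0.8 × 19.36 = 15.49. True SE of the balanced comparison: √(15.49 × 2/10) = 1.76.
- The arm-only residual also contains the strata: 20 × 0.2 × 19.36 / 18 = 4.30. Expected residual variance is 15.49 + 4.30 = 19.79, giving a reported SE of √(19.79 × 2/10) = 1.99.
- Simulation agrees: reported 1.99 against true 1.77 unadjusted; 1.76 against 1.77 adjusted.
- Unadjusted type I error is about 2% instead of 4%. The 96% interval (matching the 0.04 threshold) is about 8.7 points wide unadjusted and 7.75 adjusted.

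**3. Power with and without the two factors.** Weighted least squares, t-test at 0.04, 6-point effect, 40,000 replicates per setting, equal weights:

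| Clinics | R² | Arm only | Arm + CDRN + BP HOME |
|---|---|---|---|
| 20 | 0 | 79.2% | 78.7% |
| 20 | 0.1 | 80.2% | 82.9% |
| 20 | 0.2 | 80.8% | 86.8% |
| 20 | 0.3 | 81.8% | 90.8% |
| 28 | 0.1 | 92.9% | 94.2% |
| 28 | 0.2 | 94.0% | 96.5% |

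An analytic check for the adjusted model uses residual SD 4.4√(1 − R²) and 16 df. At R² = 0.2 the noncentrality is 6 / 1.76 = 3.41 and power is 87.0%.

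**4. Unequal weights (20 clinics, R² = 0.2).** Lognormal weights, arm-only figure first:

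| Weights | True SE | Power | Type I error | Size-corrected power |
|---|---|---|---|---|
| Match true variances, CV 0.6 | 1.62 vs 1.57 | 88.3% vs 93.5% | about 2% vs 4% | not needed |
| Unrelated to true variances, CV 0.6 | 2.06 vs 1.96 | 78.2% vs 84.8% | 4.6% vs 6.3% | 76.7% vs 79.5% |
| Unrelated to true variances, CV 1.0 | 2.38 vs 2.16 | 76.8% vs 83.4% | 8.5% vs 9.4% | 64.1% vs 70.6% |

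The true SE falls with adjustment in every row, because balance in counts is not balance in weight.

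**5. Cost if the strata explain nothing (R² = 0).** The loss is 0.4 to 1.5 points of power. The worst case found was odd cells (5/5/5/5) that leave the arms uneven on BP HOME: 79.2% to 76.7% with equal weights, and 89.1% to 86.1% with matched weights (CV 0.6).

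**The case against.** **The estimate itself may lose nothing.** With equal weights the true SE is the same with and without strata terms. The unadjusted test is merely conservative, and its power does not fall below the R² = 0 figure. This stands for equal weights: the loss there is an overstated SE and forgone power. The planned weights are unequal, however, and then the estimate is also less precise, by about 3% in SE with matched weights (1.62 vs 1.57).

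**R² is assumed.** The outcome is a within-clinic change, so stable level differences between CDRNs are already removed. The plan's remark on CDRN infrastructure concerns effect modification, not prognosis. BP HOME reaches only participating patients, which may dilute its effect on a clinic-wide rate. All of this stands, so the conclusion is conditional and given as a range.

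**Adjustment raises type I error when weights are wrong** (4.6% to 6.3%, and 8.5% to 9.4%). True, but the cause is the weights: at R² = 0 with CV 0.6 the error is already about 6 to 7% with either model. Omitting the strata offsets this by accident. Power comparisons in those settings should be read only after size correction.

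**A sensitivity model already adjusts.** It covers BP HOME and, if health systems sit within CDRNs, perhaps CDRN indirectly. This softens the point, but that model does not decide Test 1.

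**One estimator serves all three tests.** CDRN cannot be adjusted for against usual care, and adjusting Test 1 alone means the three pairwise estimates need not agree with one another. That would be a coherent reason, but the plan does not state it. Test 1 is randomised and has its own threshold, so it can be modelled on its own terms.

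**Conclusion.** The concern holds. The primary Test 1 model omits both factors on which randomisation was stratified, and no stated model names both as main effects. The consequence is conditional: at 20 clinics with equal weights, adding them gains about 3, 6 and 9 points of power at R² 0.1, 0.2 and 0.3. At 28 clinics the gain is 1.3 points at R² 0.1 and 2.5 at R² 0.2. If the strata explain nothing, it costs 0.4 to 1.5 points, at most about 3 with uneven odd-sized strata.

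This is not a bias. With equal or correct weights the unadjusted test errs on the conservative side (type I error 2.2 to 3.0% at R² 0.2). With weights unrelated to the true variances that direction is not assured, and strata terms do not repair it. The figures rest on the planning SD of 4.4, two-sided testing, the assumed R² and the assumed BP HOME split. Results were similar with cells 8/2/8/2 and with nearly all the strata effect placed on CDRN. The change is worth making, but validity does not depend on it.

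**What to change.** For Test 1 only, add CDRN and BP HOME participation as main effects to the primary weighted regression of the 6-month change on arm. Report the unadjusted comparison as the sensitivity analysis. Leave Tests 2 and 3 as planned, since the usual-care datamarts come from other CDRNs. No baseline covariate is requested, because baseline control already enters through the change score.

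If the unadjusted model stays primary, state why the stratification factors are omitted and name CDRN explicitly in the adjusted sensitivity model. Either way, fix the choice before results by arm are seen.

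The cost is analysis-plan wording and 2 of 18 residual degrees of freedom at 20 clinics. Both factors are known at randomisation, so no new data are needed.
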